### 4.3 Per-protocol set

The per-protocol set (PPS) consists of all subjects who, in addition to the FAS criteria, had no major protocol deviation (as defined in the section 4.5 and finalised during the blind data review meeting).

The subjects in the PPS will be analysed based on the treatment that they were randomised to.

Subjects who received blood transfusion will be censored from their first transfusion date for the PPS. All efficacy and PK data considered as censored data will not be part of summary tables and figures but will be listed as other data and identified with a censor flag.

### 4.4 Other Analysis Sets

For the purposes of tables and listings further four analysis population are defined:

- Screened population (all screened subjects)
- All randomised subjects (all randomised subjects)
- Modified full analysis set (optional): The modified FAS will consist of all subjects of FAS with
  no major Covid-19 related protocol deviation. The population will be defined depending of the
  number of covid-19 subjects and the impact on the analyses. The subjects in the modified FAS
  will be analysed based on the treatment that they were randomised to.

### 4.5 Protocol Deviations

The protocol deviations, classified as major by Vifor in the Project Specific Protocol Deviation List version 7.0 dated 26 November 2021 will be identified for all subjects by either site monitoring, medical review processes or programming and confirmed prior to or at the Data Review Meeting at the latest.

Population	Category	Sub category	Description	Vifor's	l
------------	----------	--------------	-------------	---------	---

				classification
PPS	2. Study Conduct/ Procedures	A. Inclusion/ Exclusion Criteria	Failure to complete inclusion criteria #1	Major
PPS	2. Study Conduct/ Procedures	B. Screening	Safety and Haematology     Laboratory samples not taken     at screening and baseline visit     prior to first dosing	Major
PPS	2. Study Conduct/ Procedures	B. Screening	9. Safety and Haematology Laboratory samples: results needed for eligibilty confirmation missing at screening and baseline visit prior to first dosing.	Major
PPS	2. Study Conduct/ Procedures	B. Screening	21. Randomization errors (e.g. incorrect randomization process interaction with IVRS system) resulting in incorrect allocation of the study therapy	Major
PPS	2. Study Conduct/ Procedures	D. Study Restrictions/ Withdrawal Criteria	Non-compliance with protocol restrictions (e.g. use of prohibited medication or prohibited treatment therapy)	Major
PPS	2. Study Conduct/ Procedures	D. Study Restrictions/ Withdrawal Criteria	2. Non-compliance with subject withdrawal criteria defined in the protocol (i.e. subject continued in study but should have been withdrawn).	Major
PPS	2. Study Conduct/ Procedures	E. Dose Formulation/ Dose Administration	2. Incorrect IMP dose intake: Patient took less than 80% of prescribed doses or took more than 105% of prescribed doses. To be assessed during the course of the study (V3 to V8)	Major
PPS	2. Study Conduct/ Procedures	E. Dose Formulation/ Dose Administration	3. Incorrect subject IMP kit given OR wrong dose regimen (total daily dose) assigned based on screening body weigth	Major

All protocol deviations will be presented in the data listings, including the nature of the protocol deviation, non-important or important.

### 5 DESCRIPTION OF THE STATISTICAL ANALYSIS

This section describes the statistical analyses, presentation of the results, and the study endpoints/measures that will be collected and/or derived during the study at the time points specified in the Schedule of Events (see section 2.2).

### 5.1 General Considerations

The software used for all summary statistics and statistical analyses will be SAS® Version 9.4 or later (SAS Institute, Inc.).

Derived datasets will be generated by the Biostatistics Department from the Clinical Interchange Standard Consortium (CDISC) Study Data Tabulation Model (SDTM [version 3.2]) datasets in accordance with CDISC ADaM version 2.1 and the ADaM Implementation Guide v1.1.

The two cohorts (adults/adolescents) will be analysed the same way into 2 separated analyses, if 5 or more adolescents are randomised into the study. Otherwise, a pooled analysis of adult and adolescent subjects will be performed.

The treatment groups will be displayed as:

- 1. VIT-2763 QD
- 2. VIT-2763 BID
- Placebo

If at least 1 subject is randomised in each body weight category, summary statistics will be repeated in each body weight category.

There is no formal statistical level for this study, and all analyses are considered descriptive.

### 5.1.1 Standard Descriptive Statistics

### Continuous Variables

Unless specified otherwise, the following standard descriptive statistics by treatment group will be obtained for continuous variables: number, mean, standard deviation, median, inter-quartile range and range. The minimum and maximum will be reported to the same number of decimal places as the raw data recorded in the database. Mean, median, inter-quartile range will be displayed to one more decimal place than collected value and standard deviation will be displayed to two more decimal place than collected value.

### Categorical Variables

Unless specified otherwise, the following standard descriptive statistics by treatment group will be presented for categorical values: total number of available values and missing values, number of values

in each category and the corresponding percentage of the total number of values available will be calculated. The percentage will be displayed using two decimals.

Percentages will be calculated using the total subjects per randomised treatment group, except for outputs in the SAF, where percentages are based on the total subjects per actual treatment group.

### 5.1.2 Definition of Baseline, Visits and Visit Windows

The baseline will be defined as the last available (non-missing) value before the first administration of study drug except for parameters listed below:

- PD measurements (serum iron, serum ferritin, unsaturated iron binding capacity, calculated transferrin saturation). Baseline will be collected during screening period within the biochemistry sample.
- For following parameters, the baseline will be defined as the value at Visit 3 2h post-dose:

PD measurements (serum transferrin).

Study day 1 is defined as the day of the first study drug administration. For analysis relative day, if considered date less than first study drug administration date, then analysis relative day will be considered date minus first study drug administration date, otherwise, it will be considered date minus first study drug administration date + 1.

### 5.1.3 Analysis Assessment Windows

Table 5 describes the Analysis Assessment Windows that will be used in all analyses.

Table 5 Analysis Assessment Windows

Visit Label	Planned visits (Protocol Specified)	Analysis Assessent Window	Target Day
Baseline*		<=1 Day*	1
Baseline 2h post-dose **	± 1 days	Day 1	1
Week 1	± 1 days	From Day 2 to Day 10	7
Week 2	± 2 days	From Day 11 to Day 21	14
Week 4	± 3 days	From Day 22 to Day 42	28

Week 8	± 3 days	From Day 43 to Day 70	56
EOT Week 12	± 3 days	From Day 71 to Day 98	84
EOS Week 16	± 4 days	>= Day 99	112

\* For ECG, baseline value (<1 Day) will be defined during Screening visit and assessment recorded at the Visit 3 (Day 1) will be presented as "Baseline 2h post-dose".

\*\* Foi

and serum

transferrin, baseline value will be defined as the value at Visit 3 2h post-dose and will be labelled "Baseline 2h post-dose". Changes from baseline in summaries will be calculated using the baseline 2h post-dose value.

All assessments (planned and unscheduled) will be re-mapped into the analysis windows. For a parameter, if several assessments fall into the same analysis window, the closest to the target day will be considered for the analysis. When there are 2 assessments closest to the target day, the latest one will be considered for the analysis (i.e. if there are 2 visits which fall on Day 13, Day 15, the visit from Day 15 will be considered for analysis.). If in case there are 2 records with valid results which fall on same date/visit, then the average of the 2 results will be taken and an additional record will be added to be considered for analysis and flagged.

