5.4.2 Withdrawal of Subjects from Study Drug

Study drug must be stopped if there is any clinically relevant AE, laboratory abnormality, inter-current illness or health condition requiring medical treatment, or significant worsening of inter-current illness which, in the opinion of the Investigator, indicates that continued participation in the study is not in the best interest of the subject. The subject concerned will remain under follow-up and the subsequent visits should be performed in accordance with the protocol schedule. Whether the subject should receive additional doses of study treatment will be discussed with the Medical Monitor and will be decided on a case by case basis. If study drug is stopped prematurely for any one subject, the subject concerned will not be replaced.

Subjects may be withdrawn from the study drug if in the opinion of the Medical Monitor or the Investigator there would be a risk to the subject's safety if they received any further dose of study drug.

Study drug must be stopped if any of the below criteria may apply:

- A potentially life-threatening (Grade 4) anaemia according to FDA toxicity grading scale for healthy adult and adolescent volunteers including Hb <8.0 g/dl (5.0 mmol/l) for female subjects or <8.5 g/dl (5.3 mmol/l) for male subjects, and with an absolute Hb drop from baseline >2 g/dl for males and females, and confirmed by subsequent repeat ≥24 hours apart [14].
- Serum transaminases (ALT or AST) >3x ULN range and total bilirubin >2x ULN (confirmed by subsequent repeat \geq 24 hours apart).
- ALT or AST >3x ULN (confirmed by subsequent repeat ≥24 hours apart) with the appearance or worsening of symptoms felt by the Investigator to be potentially related to hepatic inflammation, such as fatigue, nausea, vomiting, right upper quadrant pain or tenderness, fever, rash, or eosinophilia.

- Major protocol deviations, including noncompliance or lost to follow-up.
- Use of a non-permitted concomitant medication.
- Participation in any other clinical study during the duration of this clinical study.
- Loss of ability to freely provide consent through imprisonment or involuntary incarceration for treatment of either a psychiatric or physical (e.g., infectious disease) illness.
- Inability to comply with the protocol or study procedures.

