8.2 End of Treatment (or Early Discontinuation) Procedures

A visit will take place on completion of the treatment or early discontinuation/withdrawal (i.e., at Week 12 (Visit 8)). All assessments should be performed as detailed in Table 1 end of treatment, V8.

Visit window for end of treatment visit is ± 3 days.

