- At Week 1 (Visit 4), Week 2 (Visit 5), Week 4 (Visit 6), Week 8 (Visit 7) and Week 12 (Visit 8), a blood test to assess Hb will be performed and analysed locally. The Hb value needs to be available at the day of dosing before the subject is leaving the hospital, and will be documented in the eCRF. In addition, a urine pregnancy test will be drawn.
- Urine will be taken for urine pregnancy and test urinalysis (pH, protein, glucose, ketone, blood, spot urine for assessment of protein/creatinine and albumin/creatinine ratio), blood samples for haematology and clinical chemistry (all visits) and coagulation (Visits 6 and 8).
- Dosing will only be done in subjects for whom the urine pregnancy test is negative in females of childbearing potential. In case of a Grade 4 including Hb <8.0 g/dl (5.0 mmol/l) for female subjects or <8.5 g/dl (5.3 mmol/l) for male subjects, and with an absolute Hb drop from baseline >2 g/dl for males and females, and confirmed by subsequent repeat ≥24 hours apart, study drug will not be re-dispensed.
- Subjects will bring back the study medication dispensed to them at the previous visit
 and returned drug will be documented. Subjects will be dispensed new study drug and
 will take the first morning dose in the hospital as described in the 'Treatment' section.
 Approximately 2-3 hours after dosing a 12-lead ECG will be done, blood will be taken
 for PK (selected visits) and PD measurements (all visits),
- In subjects that have consented for genotyping and biomarker sampling an additional blood sample will be taken on Visit 8 only.

If subject withdraws prematurely, all assessments at V8 should be performed, if possible.

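### SAP 5.1.3 chooses by-visit values by study day alone, so off-drug values can fill the Week 8 and EOT Week 12 rows and the early-discontinuation value can be displaced

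*SAP*

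**What the plan says.** **Selection of values.** SAP 5.1.3 states: "Table 5 describes the Analysis Assessment Windows that will be used in all analyses". It continues: "All assessments (planned and unscheduled) will be re-mapped into the analysis windows". When a window holds more than one value, the rule is that "if several assessments fall into the same analysis window, the closest to the target day will be considered for the analysis"; ties go to the later value. The Week 8 window is "From Day 43 to Day 70" (target Day 56) and the EOT Week 12 window is "From Day 71 to Day 98" (target Day 84). No condition refers to whether the subject was still taking study drug.

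**What is collected after stopping.** For a subject who stops study drug, Protocol 5.4.2 says: "The subject concerned will remain under follow-up and the subsequent visits should be performed in accordance with the protocol schedule". Protocol 8.2 says: "A visit will take place on completion of the treatment or early discontinuation/withdrawal", with the Visit 8 assessments. Protocol 9.1.4 says: "If subject withdraws prematurely, all assessments at V8 should be performed, if possible".

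**Exclusions and on-treatment wording.** SAP 4.2 and 4.3 censor efficacy and PK data from the first transfusion. The ECG shift table in SAP 5.7.3 is worded as on-treatment. No other visible safety or iron table is. For ECG and vital signs, SAP 5.7.3 and 5.7.4 choose the value closest to the actual visit date, which differs from the target-day rule in 5.1.3.

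**The concern.** Changes in laboratory tests, vital signs and ECG are primary endpoints. Several drug-stopping criteria in Protocol 5.4.2 are confirmed haemoglobin, transaminase or bilirubin findings, so values at the time of stopping are among the most informative safety data in the trial. A rule based on study day alone can move such a value out of the change-from-baseline tables. For a subject who stays on the schedule, it can also show a later off-drug value in a row labelled end of treatment. If the change recovers off drug, the active arm is pulled toward no change.

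The iron tables have a further problem. Samples are meant to be taken about 2 hours after dosing, which has no meaning once dosing has ended. Protocol 1.2.3 describes the Phase 1 iron effect as temporary (4 to 12 hours after dosing) and gives a Day 7 geometric mean half-life of 2.61 to 5.26 hours.

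**Working it through.** **Inputs.** Windows and targets come from SAP Table 5. Scheduled visits fall on Days 7, 14, 28, 56 and 84 (Protocol Table 1). Possible early stop days run from Day 2 to Day 83, which is 82 days.

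| Row | Window (days) | Target | Stop days before target | Stop days after target |
|---|---|---|---|---|
| Week 1 | 2–10 | 7 | 5 | 3 |
| Week 2 | 11–21 | 14 | 3 | 7 |
| Week 4 | 22–42 | 28 | 6 | 14 |
| Week 8 | 43–70 | 56 | 13 | 14 |
| EOT Week 12 | 71–98 | 84 | 13 | not an early stop |
| Total | | | 40 | 38 |

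With the four visit days 7, 14, 28 and 56: 40 + 38 + 4 = 82.

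**Step 1: reproduce the SAP's own example.** Days 13 and 15 are each 1 day from Day 14. The tie goes to the later value, so Day 15 is used, as the SAP says.

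**Step 2: subject leaves the study, and the stopping assessment is the last one.**
- Stop after the target: the scheduled visit in that window is at distance 0, so the stopping value is displaced. 3 + 7 + 14 + 14 = 38 days; 38/82 = 46%.
- Stop before the target: nothing nearer exists, so the value is kept under that week's label. 5 + 3 + 6 + 13 + 13 = 40 days.
- Stop on a visit day (4 days): the stopping value is the visit value.
- No later off-drug treatment-period visit exists. Examples: a Day 35 value gives way to Day 28; a Day 50 value is kept as Week 8.

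**Step 3: subject stops drug, has a stopping assessment, and stays on schedule.**
- Every window then holds a visit at distance 0, so the stopping value is displaced on all 40 + 38 = 78 non-visit days. On 38 of them an earlier on-drug visit replaces it; on 40 a later off-drug visit does.
- The EOT Week 12 row is off-drug for all 82 stop days. The Week 8 row is off-drug for the 54 stop days from Day 2 to Day 55.
- Example: stop on Day 50. Day 50 is displaced, and the off-drug Day 56 and Day 84 values appear as Week 8 and EOT Week 12.

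**Step 4: sensitivity to visit timing.** Let scheduled visits vary uniformly within the protocol windows (±1, ±2, ±3, ±3, ±3 days; an assumption). Among non-visit stop days, the stopping value is displaced in about 87% of cases for subjects who stay and about 42% for those who leave.

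**Step 5: weight of one subject.** In an adult active arm of 8, one subject is 1/8 = 12.5%. If all 36 planned subjects were adults, an active arm would hold 36 × 8/20 = 14.4, and one subject is about 1/14 = 7%. If the off-drug change is zero (assumption), a true mean iron change D in an arm of 8 with one off-drug subject appears as 7/8 × D = 0.875D.

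**The case against.** The strongest case on the other side has five parts.

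- **The value is not lost.** All laboratory results are listed, and any abnormal post-baseline laboratory value counts in the overall summary (SAP 5.7.2). An abnormality that changes study treatment points to an AE report (Protocol 10.5.4 and 10.5.6), and TEAEs leading to treatment discontinuation are tabulated (SAP 5.7.1). This stands. None of it puts the value back into the change-from-baseline tables, and the laboratory shift table uses an undefined endpoint measurement that could itself be off-drug.
- **The PPS acts as an on-treatment analysis.** Intake below 80% is a major deviation (SAP 4.5). With a Day 84 visit and weight under 60 kg, expected intake is 83 × 2 + 1 = 167 capsules, and 80% is 133.6. Two capsules a day give 132 by Day 66, so a stop by then would exclude the subject. This holds in part, for iron. If the stopping visit is taken as the EOT date in SAP 5.5, compliance can look complete. Safety tables use only the safety set.
- **Retaining off-drug values suits an intention-to-treat set.** True, so the all-data tables should stay.
- **The two protocol instructions concern different subjects.** Section 5.4.2 requests no extra stopping assessment, and 8.2 is loosely worded because it equates the visit with Week 12. Displacement in Step 3 therefore rests on reading 8.2 as covering drug discontinuation. The off-drug Week 8 and Week 12 rows do not depend on that reading.
- **Other rules may apply.** Protocol 12.9.1 has an unclear right-censoring sentence that mentions premature withdrawal. The visible SAP does not carry it over, and the SAP takes precedence. Part of SAP 5.6 is redacted, but the safety and iron sections are readable and hold no such rule.

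**Conclusion.** The point holds as a cheap improvement to a descriptive plan. By-visit values are chosen without regard to treatment status, so the safety-set and FAS change-from-baseline tables offer no on-treatment view. Off-drug values enter the Week 8 and EOT Week 12 rows for any subject who stops drug and keeps attending. The stopping value is displaced whenever a nearer assessment shares its window: 38 of 82 stop days (46%) for subjects who leave, with visits on nominal days.

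A reader might infer two stronger things that the documents do not support:

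- **That the early-discontinuation value is always discarded.** Selection operates only when several values share a window. For subjects who leave, the value is kept on 40 stop days and coincides with a scheduled visit on 4 more.
- **That the anticipated 20% drop-out measures the dilution, so that D would appear as 0.8D.** That rate concerns subjects who do not complete the trial. Treating all of them as attending Week 12 off drug runs against its meaning. How many will stop drug yet stay is not stated, so only the per-subject weight can be given.

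The day counts apply the 5.1.3 rule to every measurement. For ECG and vital signs, the conflicting wording in 5.7.3 and 5.7.4 leaves the choice unclear.

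**What to change.** In SAP 5.1.3:

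1. Add an end-of-treatment / last on-treatment row, with change from baseline, to the laboratory, ECG, vital-sign and iron tables. Define it as the early-discontinuation assessment (the Week 12 visit for completers) if done within a pre-specified few days after the last dose; otherwise, the last value on or before the last-dose date. A strict last-dose-date cut-off would exclude a stopping visit held a day or more later, which is why the short allowance is needed. For iron, mark values not taken about 2 hours after a dose.
2. Flag values taken after that on-treatment cut-off. Keep the all-data by-visit tables, and repeat Week 1 to Week 12 on unflagged values if any subject has flagged ones.
3. Use one selection rule throughout by aligning the actual-visit-date wording in 5.7.3 and 5.7.4 with 5.1.3.

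Items 1 and 2 are both needed. Restricting to on-treatment values alone would still displace the stopping value on 38 of the 78 non-visit stop days, because an earlier on-drug visit is nearer the target.

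The cost is one derived flag from dates already collected, one extra row per table, and a repeat table set only if someone stopped early.

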### 5.1.4 Treatment Start/Stop Dates

If there are no treatment dates available in the administration page of the CRF, date of randomisation will be imputed as the start of treatment date, if it is known that the subject received study drug (information recorded in the administration page of the CRF or any information from monitoring).

If the end of treatment date is missing in the treatment termination page of the CRF, the earliest date between the returned date from supply accountability log page and the latest date from administration page (with no return recorded) would be imputed.

### 5.1.5 Tables and Listings Presentation

The listings will display all the data contained in the CRF, including the screen failure patients collected information if appropriate. The listings will be ordered by cohort, treatment groups, body weight and subject number.

There will be no statistical tests performed. If confidence is mentioned, the level will be 95% unless otherwise specified.

### 5.1.6 Analysis Populations

The safety set will be used for all safety analyses.

The FAS will be used for and PK concentration. The PPS will be also used

in case of any difference with FAS. The modified FAS may be used depending of the number of covid-19 subjects and the impact on analyses.

Demographics and baseline characteristics, medical history and concurrent medical conditions, prior and concomitant medications and procedure and study drug exposure and compliance will be computed on the FAS, PPS and the SS. Only sets with different attribute will be presented.

### 5.1.7 Pooling of Sites/Country

Not applicable for this study

### 5.1.8 Analysis of Subgroups

The following subgroups will be considered:

- Body weight at screening: <60 kg/ ≥ 60 kg

- Gender: Male/Female
- Race: American Indian or Alaska Native/Asian/Black or African American/Native Hawaiian or Other Pacific Islander/White/Other. Each race category will be part of subgroup analysis only if there is at least one subject in.

In case of imbalance between treatment groups regarding baseline characteristics, other subgroup analyses may be performed.

Following outputs will be repeated in each subgroup:

- Table 14.2.1.1.1 Summary statistics of other iron related parameters over time
- Table 14.2.1.5.1 Summary Statistics of Increase from Baseline in Haemoglobin by Visit
- Table 14.3.1.1.1 Overall Summary of Adverse Events
- Table 14.3.1.2.1 Treatment-emergent Adverse Events by System Organ Class and Preferred Term
- Table 14.3.1.3.1 Serious TEAEs by System Organ Class and Preferred Term
- Table 14.3.1.5.1 Serious TEAEs related to study medication by System Organ Class and Preferred Term

